10.13. Appendix 13: Abbreviations

The following is a list of abbreviations that may be used in the protocol.

	Term
Abs	absolute
ADA	antidrug antibodies
ADCC	antibody dependent cell-mediated cytotoxicity
AE	adverse event
AESI	adverse events of special interest
ALT	alanine aminotransferase
AST	aspartate aminotransferase
AUC _{168H}	area under the curve from the time of dose administration up to 168 hours
AUC _{inf}	area under the concentration-time curve from time 0 to infinity
AUC _{last}	area under the concentration-time curve from 0 to time of last measurable concentration
AUC _t	area under the concentration-time curve from 0 to time t
AV	atrioventricular
BBS	Biospecimen Banking System
β-hCG	Beta-human chorionic gonadotropin
BIA	bioelectrical impedance analysis
BUN	blood urea nitrogen
C _{av} or C _{avg}	average concentration
CDC	complement-dependent cytotoxicity
CFR	Code of Federal Regulations
CI	confidence interval
CIOMS	Council for International Organizations of Medical Sciences
CK	creatine kinase
CKD	chronic kidney disease
CL/F	apparent clearance of drug from eg, plasma
CLIA	clinical laboratory improvement amendments
C _{max}	maximum observed concentration
CO ₂	carbon dioxide (bicarbonate)
CONSORT	Consolidated Standards of Reporting Trials
COPD	chronic obstructive pulmonary disease
COVID-19	coronavirus disease 2019
CRF	case report form
CRO	contract research organization
CRP	C-reactive protein
CRU	clinical research unit
CSR	Clinical Study Report
CT	clinical trial
CTCAE	Common Terminology Criteria for Adverse Events

	Term
CYP	cytochrome P450
DC	discontinuation
DCT	data collection tool
DILI	drug-induced liver injury
DMC	data monitoring committee
DNA	deoxyribonucleic acid
DU	dispensable unit
EC	ethics committee
ECG	electrocardiogram
eCOA	electronic clinical outcome assessment
eCRF	electronic case report form
EDP	exposure during pregnancy
EMA	European Medicines Agency
E _{max}	maximal effect
EORTC	European Organisation for Research and Treatment of Cancer
ET	early termination
EU	European Union
EudraCT	European Clinical Trials Database
Fc γ	fragment crystallizable gamma
FSH	follicle-stimulating hormone
GCP	Good Clinical Practice
GDF-15	growth differentiation factor 15
GDNF	glial cell-derived- neurotrophic factor
GFR	Glomerular Filtration Rate
GFRAL	family receptor alpha-like
GGT	gamma-glutamyl transferase
HBV	hepatitis B virus
HCP	Health Care Professional
HCV	hepatitis C virus
HIPAA	Health Insurance Portability and Accountability Act
HIV	human immunodeficiency virus
HR	heart rate
HRT	hormone replacement therapy
IB	Investigator's Brochure
ICD	informed consent document
ICH	International Council for Harmonisation of Technical Requirements for Pharmaceuticals for Human Use
ID	identification
IgG1	immunoglobulin G1
IgG1 κ	immunoglobulin gamma-1 with kappa light chains
IMP	investigational medicinal product
IND	investigational new drug

	Term
INR	international normalized ratio
IP	investigational product
IP manual	investigational product manual
IPAL	Investigational Product Accountability Log
IRB	institutional review board
IRC	internal review committee
IRT	interactive response technology
IUO	investigational use only
IWR	interactive Web-based response
LBBB	left bundle branch block
LFT	liver function test
mAb	monoclonal antibody
MCH	mean corpuscular hemoglobin
MCHC	mean corpuscular hemoglobin concentration
MCV	mean corpuscular volume
MDRD	modification of diet in renal disease
MIC-1	Macrophage Inhibitory Cytokine 1
MMRM	mixed-effect model repeated measure
MRI	magnetic resonance imaging
msec	millisecond
N/A	not applicable
NAb	neutralizing antibodies
NCI	National Cancer Institute
NIMP	noninvestigational medicinal product
NOAEL	no-observed-adverse-effect level
NSCLC	non-small cell lung cancer
OL	open-label
OLT	open-label treatment
PD	pharmacodynamic(s)
PE	physical examination
PGI-C	patient global impression of change
PI	principal investigator
PK	pharmacokinetic(s)
PRO	patient reported outcome
PROMIS	Patient-Reported Outcomes Measurement Information System
PT	prothrombin time
PVC	premature ventricular contraction/complex
Q3W	3 weeks apart
Qual	qualitative
RBC	red blood cell
RN	registered nurse
RNA	ribonucleic acid

	Term
SAE	serious adverse event
SAP	Statistical Analysis Plan
SARS-CoV2	severe acute respiratory syndrome coronavirus 2
SC	subcutaneous
SMP	study monitoring plan
SoA	schedule of activities
SOP	standard operating procedure
SRSD	single reference safety document
SSID	single subject identifier
SToD	study team on demand
SUSAR	Suspected Unexpected Serious Adverse Reaction
$t_{1/2}$	terminal phase half-life
TBili	total bilirubin
TEAE	treatment-emergent adverse event
TGF β	transforming growth factor beta
T_{max}	time to reach C_{max}
ULN	upper limit of normal
US	United States
WBC	white blood cell
WOCBP	woman/women of childbearing potential

## 1. VERSION HISTORY

**Table 1. Summary of Changes**

Version/ Date	Associated Protocol Amendment	Rationale	Specific Changes
Version 1 / 13APR2021	Original 18DEC2020	N/A	N/A

## 2. INTRODUCTION

This statistical analysis plan (SAP) provides the detailed methodology for summary and statistical analyses of the data collected in **Part A** of Study C3651010 (including follow-up for Part A if a participant does not continue to Part B of the study). This document may modify the plans outlined in the protocol; however, any major modifications of the primary endpoint definition or its analysis will also be reflected in a protocol amendment. The methodology for summary and statistical analyses of the data collected in Part B of the study will be detailed in a supplemental SAP.

### 2.1. Study Objectives, Endpoints, and Estimands

Objectives	Endpoints	Estimands
Primary		
• To evaluate the early effect of PF-06946860 compared to placebo on appetite in participants with anorexia and advanced cancer.	• Change from baseline for patient reported 7-day recall Cancer-Related Cachexia Symptom Assessment–Appetite score, at week 4.	• Estimand 1 (similar to “hypothetical”) is intended to provide a population level estimate of the treatment effect on the change from baseline Appetite score for PF-06946860 compared to placebo in all evaluable participants under the scenario of no discontinuation of study intervention and without the potential confounding effects of prohibited medications, regardless of the participants’ compliance with dosing (i.e. using the Censored analysis set)
Secondary		
• To evaluate the effect of PF-06946860 compared to placebo on appetite in participants with anorexia and advanced cancer.	• Change from baseline for patient reported 7-day recall Cancer-Related Cachexia Symptom Assessment–Appetite score, at weeks 1, 2, 3, 5 and 6.	• Estimand 1, as above

Objectives	Endpoints	Estimands

 
• To evaluate the effect of PF-06946860 compared to placebo on fatigue in participants with anorexia and advanced cancer.
 
	
 
• Change from baseline for patient reported 7-day recall Cancer-Related Cachexia Symptom Assessment-Fatigue score, at weeks 1, 2, 3, 4, 5 and 6.
 
	
 
• Estimand 2 (similar to “hypothetical”) is intended to provide a population level estimate of the treatment effect on the change from baseline Fatigue score for PF-06946860 compared to placebo in all evaluable participants under the scenario of no discontinuation of study intervention and without the potential confounding effects of prohibited medications, regardless of the participants’ compliance with dosing (i.e. using the Censored analysis set)
 


 
• To characterize the safety and tolerability of repeated subcutaneous (SC) administrations of PF-06946860 compared to placebo in participants with anorexia and advanced cancer.
 
	
 
• Incidence of adverse events (AE) and laboratory abnormalities, in Part A of the study.
 
	
 
• There are no defined estimands for these endpoints and they will be analyzed using Pfizer data standards, as applicable.
 

Tertiary/Exploratory:		

 
• To evaluate the effect of PF-06946860 compared to placebo on body weight in participants with anorexia and advanced cancer.
 
	
 
• Change from baseline in body weight, at weeks 3, 4 and 6.
 
	
 
• N/A
 

 
• To explore the relationship between pain and appetite/fatigue in participants with anorexia and advanced cancer
 
	
 
• Change from baseline score for patient reported 7-day recall PROMIS-Pain 1a, Cancer-Related Cachexia Symptom Assessment-Fatigue score and Cancer-Related Cachexia Symptom Assessment-Appetite score at Weeks 1, 2, 3, 4, 5 and 6.
 
	
 
• N/A
 

 
• To assess patient global impression of change (PGI-C) of appetite and fatigue in participants with anorexia and advanced cancer
 
	
 
• PGI-C (appetite), at Weeks 4 and 6.
 
• PGI-C (fatigue), at Weeks 4 and 6.
 
	
 
• N/A
 

 
• To characterize unbound and total pharmacokinetics (PK) of PF-06946860 administered in participants with anorexia and advanced cancer
 
	
 
• Serum unbound and total concentrations of PF-06946860, on Day 1 and Weeks 3, 4 and 6.
 
	
 
• N/A
 


 
• To characterize the effect of PF-06946860 administration on circulating growth differentiation factor 15 (GDF-15) concentrations in
 
	
 
• Serum concentrations of total GDF-15; and if feasible, unbound GDF-15, on Day 1 and Weeks 3, 4 and 6.
 
	
 
• N/A
 

Objectives	Endpoints	Estimands
participants with anorexia and advanced cancer.		
● To assess the immunogenicity of PF-06946860 administered in participants with anorexia and advanced cancer.	● Incidence of antidrug antibodies (ADA) and, if applicable, neutralizing antibodies (Nab), in part A of the study.	● N/A

Additional tertiary/exploratory objectives will be evaluated using data from **Part B** of Study C3651010, as data permit. These objectives are not addressed in this SAP but will be addressed in a supplemental SAP.

### 2.1.1. Primary Estimand(s)

Estimand related to the change from baseline for the patient reported 7-day recall Appetite score (Part A):

**Estimand 1** (similar to “hypothetical”) is intended to provide a population level estimate of the treatment effect on the change from baseline Appetite score for PF-06946860 compared to placebo in all evaluable participants under the scenario of no discontinuation of study intervention and without the potential confounding effects of prohibited medications, regardless of the participants’ compliance with dosing (i.e. using the Censored analysis set).

- *Population: Patients with advanced cancer, anorexia and elevated circulating GDF-15 levels.*
- *Variable: Change from baseline for the patient reported 7-day recall Cancer-Related Cachexia Symptom Assessment–Appetite score at Week 4.*
- *Intercurrent Events:*
  - a) *Discontinuation of study intervention – Data collected after a participant has discontinued study intervention will be censored and treated as missing data.*
  - b) *Prohibited medications – Data collected after a participant has received prohibited medications, that would modulate the primary endpoint, will be censored and treated as missing data. The list of concomitant medications will be reviewed prior to database lock to determine which would be classed as “prohibited” for this estimand.*
  - c) *Inadequate compliance – Data collected after a participant has missed a dose will be censored and treated as missing data.*

*Missing data due to censoring, study withdrawal or other reasons, are assumed to be missing at random.*
- *Population level summary: Difference in mean change from baseline for the patient reported 7-day recall Cancer-Related Cachexia Symptom Assessment–Appetite score at Week 4 between PF-06946860 and placebo.*

This estimand will similarly be applied to the change from baseline at Weeks 1, 2, 3, 5 and 6.

### **2.1.2. Secondary Estimand(s)**

Estimand related to the change from baseline for the patient reported 7-day recall Fatigue score (Part A):

**Estimand 2** will be similar to **Estimand 1**, except for the following: -

- *Variable: Change from baseline for the patient reported 7-day recall Cancer-Related Cachexia Symptom Assessment–Fatigue score at Weeks 1, 2, 3, 4, 5 and 6.*
- *Population level summary: Difference in mean change from baseline for the patient reported 7-day recall Cancer-Related Cachexia Symptom Assessment–Fatigue score at Week 4 between PF-06946860 and placebo.*

Estimands related to safety and tolerability:

*There are no defined estimands for the incidence of treatment emergent adverse events and laboratory abnormalities, and these endpoints will be analyzed using Pfizer data standards as applicable.*

### **2.1.3. Additional Estimand(s)**

Estimands related to tertiary/exploratory objectives:

*Tertiary/exploratory endpoints may be analyzed using similar estimands or analyzed in a descriptive manner without reference to an estimand. Other supporting estimands may be used for some of the primary and secondary endpoints as a means to examine the robustness of results, compare to available literature and/or be used for future study planning as needed.*

Additional estimand related to the change from baseline for the patient reported 7-day recall Appetite score (Part A):

**Estimand 3** (similar to “treatment policy”) may be used, dependant on the amount of censored data (based on a blinded review prior to database lock), to assess the robustness of the treatment effect on the primary endpoint. It is intended to provide a population level estimate of the treatment effect on the change from baseline Appetite score for PF-06946860 compared to placebo in all evaluable participants without regard to discontinuation of study intervention or administration of prohibited medications, regardless of the participants’ compliance with dosing (i.e. using the Complete analysis set).

- Population: Patients with advanced cancer, anorexia and elevated circulating GDF-15 levels.
- Variable: Change from baseline for the patient reported 7-day recall Cancer-Related Cachexia Symptom Assessment–Appetite score at Week 4.
- Intercurrent Events:
  - a) Discontinuation of study intervention – All data collected, regardless of a participant’s discontinuation of study intervention, will be included in the analysis.
  - b) Prohibited medications – All data collected, regardless of a participant’s use of prohibited medications, will be included in the analysis.

- c) Inadequate compliance – All data collected, regardless of a participant's compliance (i.e. missed doses), will be included in the analysis.
- Population level summary: Difference in mean change from baseline for the patient reported 7-day recall Cancer-Related Cachexia Symptom Assessment–Appetite score at Week 4 between PF-06946860 and placebo.

This estimand will similarly be applied to the change from baseline at Weeks 1, 2, 3, 5 and 6.

## 2.2. Study Design

*This is a Phase 1b study in patients with advanced cancer, anorexia and elevated circulating GDF-15 levels with the primary purpose of assessing the effect of PF-06946860 administration on appetite.*

*The study will be conducted in 2 parts. The initial 6-week treatment period will be a randomized, double-blind, placebo-controlled, parallel group study. Participants who meet the entry criteria will be randomized to study drug (PF-06946860 or placebo). The 6-week double-blind period will consist of a total of 2 SC doses, administered 3 weeks apart (Q3W). The 6-week double-blind treatment period will be followed by optional open-label treatment (OLT) with PF-06946860 of up to 18 weeks; the total duration of treatment would, therefore, be up to 24 weeks.*

*Approximately 40 participants will be randomly assigned to investigational product such that approximately 30 evaluable participants complete the 6-week double-blind portion of the study. The study will be randomized in approximately a 2:1 ratio (27 active: 13 placebo).*

[figure not shown]
*Potential participants will attend 2 clinic visits (Screening and Randomization) with the investigator.*

*All study visits following Randomization may be conducted by a visiting Health Care Professional (HCP) at the patient's home. Should the participant elect, at Randomization, to have all subsequent Part A study visits carried out at the investigator site rather than at home, this preference may be accommodated.*

*During the week 4 TeleHealth consult, the investigator and participant will decide whether to continue with the optional open-label treatment period. Participants opting to continue to the OLT period will receive their first dose of open-label PF-06946860 at the week 6 visit, coinciding with the last visit of the double-blind portion of the study.*

*Follow-up contact with all participants (whether participating in the 6-week double-blind only, or the OLT period) will be scheduled to occur at least 28 days and up to 35 days after the last administration of IP. For study Part A, this contact may be done via a phone call, telehealth or in the clinic. Additional follow-up may be conducted for safety evaluation, at the discretion of the investigator.*

**Figure 1 Schema**

This SAP relates to the 6-week double blind (Part A) portion of the study.

### **3. ENDPOINTS AND BASELINE VARIABLES: DEFINITIONS AND CONVENTIONS**

For all endpoints, baseline is defined as the measurement taken on Day 1 (unless otherwise specified) or, if that is not available, the last-pre-dose measurement at screening will be used, where appropriate.

For those participants continuing into Part B of the study, only data collected prior to dosing at Week 6 will be included in the summary and statistical analyses of Part A of the study.

#### **3.1. Primary Endpoint(s)**

- *Change from baseline for patient reported 7-day recall Cancer-Related Cachexia Symptom Assessment–Appetite score, at Week 4*

*The Cancer-Related Cachexia Symptom Assessment-Appetite is a self-reported questionnaire that measures the severity of anorexia. It was developed based on qualitative research with patients as well as review of literature and other existing relevant measures. The measure consists of 1 question that asks study participants to rate their appetite over the past 7 days from 0- “no appetite” to 10- “very good appetite”. The assessments will be completed electronically by study participants at home, or at the clinic.*

#### **3.2. Secondary Endpoint(s)**

- *Change from baseline for patient reported 7-day recall Cancer-Related Cachexia Symptom Assessment–Appetite score, at Weeks 1, 2, 3, 5 and 6*

See section 3.1.

- *Change from baseline for patient reported 7-day recall Cancer-Related Cachexia Symptom Assessment-Fatigue score, at Weeks 1, 2, 3, 4, 5 and 6*

*The Cancer-Related Cachexia Symptom Assessment-Fatigue is a self-reported questionnaire that measures the severity of fatigue. It was developed based on qualitative research with patients as well as review of literature and other existing relevant measures. The measure consists of 1 question that asks study participants to rate their fatigue over the past 7 days from 0- “no fatigue” to 10- “worst possible fatigue”. The assessments will be completed electronically by study participants at home, or at the clinic.*

- *Incidence of adverse events and laboratory abnormalities, in Part A of the study*

See section 3.5.

#### **3.3. Other Endpoint(s)**

- *Change from baseline in body weight, at Weeks 3, 4 and 6*

Body weight will be recorded using an electronic scale (provided to the participant for their use at home). During each weight measurement, from Randomization onward, body composition data (including total body water, fat mass and fat-free mass, if possible) will be captured via bioelectrical impedance analysis (BIA), as feasible.

- *Change from baseline score for patient reported 7-day recall PROMIS-Pain 1a at Weeks 1, 2, 3, 4, 5 and 6*

The PROMIS Pain 1a is a self-reported measure that assesses the intensity of the participant's pain in the past 7 days from 0- "no pain" to 10- "worst imaginable pain".

- *PGI-C (appetite), at Weeks 4 and 6 and PGI-C (fatigue) at Weeks 4 and 6*

The PGI-C is a measure consisting of 2 questions that asks study participants to rate the overall change in their symptoms of appetite and fatigue since they started the study on a 7 point verbal rating scales that ranges from "Much better" to "Much worse".

The PGI-C (appetite and fatigue) categories will be combined to produce a 5-point scale as defined below:-

Category	Definition
Much Better	1
Somewhat Better	2-3
No Change	4
Somewhat Worse	5-6
Much Worse	7

- *Serum unbound and total concentrations of PF-06946860, on Day 1 and Weeks 3, 4 and 6.*
- *Serum concentrations of total GDF-15; and if feasible, unbound GDF-15, on Day 1 and Weeks 3, 4 and 6.*

Relative change from baseline (i.e. post-dose / baseline) will be derived at each post-baseline timepoint.

- *Incidence of ADA and, if applicable, NAb, in part A of the study.*
- *Change from baseline in body composition endpoints, at Weeks 3, 4 and 6*

During each weight measurement from Randomization onward, and using electronic scale provided to the participant, body composition data (including total body water, fat mass and fat-free mass, if possible) will be captured via bioelectrical impedance analysis (BIA), as feasible.

### **3.4. Baseline Variables**

Not applicable.

### **3.5. Safety Endpoints**

#### **3.5.1. Adverse Events**

An AE is considered treatment emergent (TEAE), relative to a given treatment, if the event starts during the effective duration of treatment, i.e. starting on, or after, the date and time of the first dose, but before the end of Part A (i.e. Week 6 for subjects continuing to Part B; or follow-up contact (28-35 days after last dose), for those subjects not continuing to Part B of the study)).

A 3-tier approach for summarizing AEs will not be used due to the low number of participants planned to be recruited.

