
To characterize the unbound and total PK of PF-06946860 administered in participants with anorexia and advanced cancer, during the open-label treatment period.	
Serum unbound and total concentrations of PF-06946860, at Weeks 12, 18 and 24.	
• N/A

To characterize the effect of PF-06946860 administration on circulating GDF-15 concentrations in participants with anorexia and advanced cancer, during the open-label treatment period.	
Serum concentrations of total GDF-15; and if feasible, unbound GDF-15, at Weeks 12, 18 and 24.	
• N/A

Objectives	Endpoints	Estimands

To assess the immunogenicity of PF-06946860 administered in participants with anorexia and advanced cancer, during the open-label treatment period.	
Incidence of ADA and, if applicable, NAb, in Part B of the study.	
N/A

Overall Design

This is a Phase 1b study in patients with advanced cancer, anorexia and elevated circulating GDF-15 levels. The study will be conducted in 2 parts. The initial 6-week treatment period will be a randomized, double-blind, placebo-controlled, parallel group study. Participants who meet the entry criteria will be randomized to study drug (PF-06946860 or placebo). The 6-week double-blind dosing period will consist of a total of 2 SC doses, administered 3 weeks apart (Q3W). The 6-week double-blind treatment period will be followed by optional open-label treatment (OLT) with PF-06946860 of up to 18 weeks.

Potential participants will attend at least 2 clinic visits (Screening and Randomization) with the investigator. The Screening visit will occur no more than 28 days and no less than 5 days, prior to Randomization. The 5-day minimum duration between Screening and Randomization visits will ensure that all necessary data (including GDF-15 level) are available to inform the investigator's assessment of eligibility.

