8.3.1. Time Period and Frequency for Collecting AE and SAE Information

The time period for actively eliciting and collecting AEs and SAEs (“active collection period”) for each participant begins from the time the participant provides informed consent, which is obtained before the participant’s participation in the study (ie, before undergoing any study-related procedure and/or receiving study intervention), through and including a minimum of up to the time of the final planned follow-up visit, after the last administration of the study intervention.

Follow-up by the investigator continues throughout and after the active collection period and until the AE or SAE or its sequelae resolve or stabilize at a level acceptable to the investigator and Pfizer concurs with that assessment.

For participants who are screen failures, the active collection period ends when screen failure status is determined.

If the participant withdraws from the study and also withdraws consent for the collection of future information, the active collection period ends when consent is withdrawn.

If a participant definitively discontinues or temporarily discontinues study intervention because of an AE or SAE, the AE or SAE must be recorded on the CRF and the SAE reported using the CT SAE Report Form.

Investigators are not obligated to actively seek AEs or SAEs after the participant has concluded study participation. However, if the investigator learns of any SAE, including a death, at any time after a participant has completed the study, and he/she considers the event to be reasonably related to the study intervention, the investigator must promptly report the SAE to Pfizer using the CT SAE Report Form.

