10.3.1. Definition of AE

AE Definition

• An AE is any untoward medical occurrence in a patient or clinical study participant, temporally associated with the use of study intervention, whether or not considered related to the study intervention.• NOTE: An AE can therefore be any unfavorable and unintended sign (including an abnormal laboratory finding), symptom, or disease (new or exacerbated) temporally associated with the use of study intervention.

Events Meeting the AE Definition

• Any abnormal laboratory test results (hematology, clinical chemistry, or urinalysis) or other safety assessments (eg, ECG, radiological scans, vital sign measurements), including those that worsen from baseline, considered clinically significant in the medical and scientific judgment of the investigator. Any abnormal laboratory test results that meet any of the conditions below must be recorded as an AE:
• Is associated with accompanying symptoms.• Requires additional diagnostic testing or medical/surgical intervention.• Leads to a change in study dosing (outside of any protocol-specified dose adjustments) or discontinuation from the study, significant additional concomitant drug treatment, or other therapy.• Exacerbation of a chronic or intermittent preexisting condition including either an increase in frequency and/or intensity of the condition.• New conditions detected or diagnosed after study intervention administration even though it may have been present before the start of the study.• Signs, symptoms, or the clinical sequelae of a suspected drug-drug interaction.• Signs, symptoms, or the clinical sequelae of a suspected overdose of either study intervention or a concomitant medication. Overdose per se will not be reported as an AE/SAE unless it is an intentional overdose taken with possible suicidal/self-harming intent. Such overdoses should be reported regardless of sequelae.

Events NOT Meeting the AE Definition

- Any clinically significant abnormal laboratory findings or other abnormal safety assessments which are associated with the underlying disease, unless judged by the investigator to be more severe than expected for the participant's condition.
- The disease/disorder being studied or expected progression, signs, or symptoms of the disease/disorder being studied, unless more severe than expected for the participant's condition.

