- Medical or surgical procedure (eg, endoscopy, appendectomy): the condition that leads to the procedure is the AE.
- Situations in which an untoward medical occurrence did not occur (social and/or convenience admission to a hospital).
- Anticipated day-to-day fluctuations of preexisting disease(s) or condition(s) present or detected at the start of the study that do not worsen.
- Worsening of signs and symptoms of the malignancy under study should be recorded as AEs in the appropriate section of the CRF. Disease progression assessed by measurement of malignant lesions on radiographs or other methods should not be reported as AEs.

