The investigator will make an assessment of intensity for each AE and SAE reported during the study and assign it to 1 of the following categories:

GRADE	Clinical Description of Severity
1	MILD adverse event
2	MODERATE adverse event
3	SEVERE adverse event
4	LIFE-THREATENING consequences; urgent intervention indicated
5	DEATH RELATED TO adverse event

An event is defined as "serious" when it meets at least 1 of the predefined outcomes as described in the definition of an SAE, NOT when it is rated as severe.

Assessment of Causality

- The investigator is obligated to assess the relationship between study intervention and each occurrence of each AE/SAE.
- A "reasonable possibility" of a relationship conveys that there are facts, evidence, and/or arguments to suggest a causal relationship, rather than a relationship cannot be ruled out.
- The investigator will use clinical judgment to determine the relationship.

- Alternative causes, such as underlying disease(s), concomitant therapy, and other risk factors, as well as the temporal relationship of the event to study intervention administration, will be considered and investigated.
- The investigator will also consult the IB and/or product information, for marketed products, in his/her assessment.
- For each AE/SAE, the investigator **must** document in the medical notes that he/she has reviewed the AE/SAE and has provided an assessment of causality.
- There may be situations in which an SAE has occurred, and the investigator has minimal information to include in the initial report to the sponsor. However, **it is very important that the investigator always make an assessment of causality for every event before the initial transmission of the SAE data to the sponsor.**
- The investigator may change his/her opinion of causality in light of follow-up information and send an SAE follow-up report with the updated causality assessment.
- The causality assessment is one of the criteria used when determining regulatory reporting requirements.

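### The SAP's treatment-emergent rule goes by start date alone, so a pre-dose AE that worsens after dosing counts or not depending on how the site records it

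*SAP*

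**What the plan says.** SAP 3.5.1 gives the only definition of a treatment-emergent AE in the two documents: "An AE is considered treatment emergent (TEAE), relative to a given treatment, if the event starts during the effective duration of treatment". The window opens at the first dose. It closes at Week 6 for participants who go on to Part B and at the follow-up contact for the others. The section does not mention an event that begins earlier and gets worse.

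Protocol 8.3.1 says that active collection "begins from the time the participant provides informed consent". The synopsis gives the length of the pre-dose period: "The Screening visit will occur no more than 28 days and no less than 5 days, prior to Randomization".

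Three parts of protocol Appendix 3 bear on what happens when such an event worsens:

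- Section 10.3.1 lists this among the events that meet the AE definition: "Exacerbation of a chronic or intermittent preexisting condition including either an increase in frequency and/or intensity of the condition".
- Section 10.3.1 also lists what is not an AE, including: "Anticipated day-to-day fluctuations of preexisting disease(s) or condition(s) present or detected at the start of the study that do not worsen".
- Section 10.3.3 tells the investigator to grade each AE and "assign it to 1 of the following categories". Its follow-up instructions send new or changed information to the CRF entry already made for the event.

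The Part A safety endpoint is worded as AE incidence. SAP 2.1.2 and protocol 9.1.1 both describe it as treatment-emergent. SAP 6.6.1 leaves the AE tables to sponsor reporting standards, which are not reproduced.

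**The concern.** In advanced cancer, with systemic antineoplastic therapy permitted, some participants may well have an AE open at Day 1. For those events the safety question is whether they get worse on treatment, and a start-date rule does not ask it.

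Two things are at stake. First, compared with a definition that includes worsening, the rule can only lower the TEAE count and the maximum grade in an arm; it can never raise them. Its effect on the difference between arms depends on where the worsening occurs, which is unknown. Second, the result comes to depend on recording habits: two sites that see the same clinical course can produce different TEAE counts. AE incidence in Part A is a secondary endpoint, and the risk assessment in protocol 2.3.1 describes this trial as the first safety experience with the antibody across varied cancers and anti-tumor treatments.

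**Working it through.** The documents give no rate of pre-dose AEs or of their worsening, so there is no planned figure to reproduce. The check is a comparison of the text, followed by a scale calculation.

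**Step 1: can an AE exist before the TEAE window opens?** Yes. Collection starts at consent (protocol 8.3.1). Screening precedes randomization by 5 to 28 days (protocol 1.1), and the first dose is given on Day 1, the randomization day (Schedule of Activities).

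**Step 2: apply the rule to one course recorded in two ways.** As an illustration, Grade 1 nausea starts in screening, is ongoing at Day 1, and becomes Grade 3 after the Day 22 dose. The SAP test is "if the event starts during the effective duration of treatment, i.e. starting on, or after, the date and time of the first dose".

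| How the site records it | Start date in the data | TEAE under SAP 3.5.1? |
|---|---|---|
| Updates the existing entry (protocol 10.3.3, follow-up) | In screening | No |
| Enters the worsening as its own AE (protocol 10.3.1) | After Day 22 | Yes |

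The course is the same and the classification is opposite.

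**Step 3: does anything in the documents settle which row applies?** No. Section 10.3.1 makes the worsening a reportable event but does not say that it needs a separate entry and onset date when an entry is already open. The follow-up text in 10.3.3 points to the existing entry but sets no onset-date rule. The instruction to give each AE one intensity category does not decide the start date either.

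**Step 4: scale.** The planned arm sizes are 27 and 13 (protocol 9.2). The change in incidence for a given AE term, or in a maximum-severity count, when k participants in an arm are reclassified is 100 × k/n percentage points:

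| k | Active (n = 27) | Placebo (n = 13) |
|---|---|---|
| 1 | 1/27 = 3.7 | 1/13 = 7.7 |
| 2 | 2/27 = 7.4 | 2/13 = 15.4 |
| 3 | 3/27 = 11.1 | 3/13 = 23.1 |

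These figures show what each participant is worth. They do not predict k. For any-TEAE incidence the change is zero if the participant has another qualifying TEAE.

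**The case against.** The strongest reply is that the protocol already catches worsening. An exacerbation is an AE, conditions present at study start are left out only if they do not worsen, and worsening signs and symptoms of the malignancy are to be recorded as AEs. Entered as an event of its own, any of these starts on treatment and satisfies SAP 3.5.1. This stands, and it limits the point to an AE already on record between consent and Day 1 that worsens under the same entry. It does not close that gap, because the only instruction about an existing entry is to update it.

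A reader might infer that worsening counts when a condition predates consent but not when it began in screening. The documents do not say so: section 10.3.1 does not tie a preexisting condition to the consent date.

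The effect on the tables also depends on sources that are not available. SAP 6.6.1 does not state that its tables are limited to TEAEs, and the sponsor standards and the CRF completion instructions may deal with the matter. That is a fair reservation. Against it, SAP 3.5.1 is the stated rule, and both documents call the endpoint treatment-emergent, so a repair in unseen material cannot be assumed.

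Finally, a worsening does not vanish from view. Every AE goes on the CRF, SAEs are reported to the sponsor whatever their TEAE status, and SAP 3.5.2 takes baseline status into account for laboratory abnormalities. Part A safety is descriptive, with no formal tests. All of this is right, and it keeps the matter to an inexpensive improvement in the safety summaries.

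**Conclusion.** The point holds in a limited form. Followed as written, SAP 3.5.1 can omit from the Part A TEAE summaries an AE that was open at Day 1 and then rose in grade or became serious, when the site updated the original entry. The same course is counted when the site opens a new one. Each participant affected is worth 3.7 points on active or 7.7 on placebo for a given AE term or maximum-severity count, and possibly nothing for any-TEAE incidence.

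This rests on two assumptions: that the tables follow SAP 3.5.1, and that no CRF instruction outside these documents requires a new entry when the grade changes.

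Two stronger readings are not supported. A reader might conclude that events beginning in screening and worsening on treatment drop out of the safety endpoint as a class. They need not, because protocol 10.3.1 allows the worsening to be entered as an AE with an on-treatment onset. A reader might also attach a rate: assuming that 10 to 30% of the 40 participants have such a worsening gives 0.10 × 40 = 4 to 0.30 × 40 = 12. Nothing in the documents anchors that range, and using it as a loss would treat every worsening as missed.

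**What to change.** In SAP 3.5.1, define a TEAE as an event that either starts on or after the first dose, or was present before the first dose and increases in CTCAE grade or becomes serious on or after it. Both limbs should use the existing Part A window.

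Two supporting steps are needed. Capture the date of the grade change, so that the second limb can be derived. Where a site has opened a new entry for the worsening, link it to the original so that one worsening is not counted twice.

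Use the same definition in the Part B supplemental SAP, where an AE that began in the double-blind period may worsen on open-label drug.

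The cost is one SAP sentence, one CRF instruction, a linkage rule and a line of derivation code. Reported TEAE incidence may be slightly higher as a result.
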